16.0 Confidentiality

16.1 Data Security:

All study personnel will be trained on and follow standard operating procedures for interacting with participants and managing data to ensure proper handling and security of data. All data will remain strictly confidential and will be stored in secured locations separately from personal identifiers. Only approved study personnel will have access to collected data. All paper documents will be stored in a locked file cabinet. We will be using either RedCap or Box (or both) to digitize and

share data. As described on the UMN RedCap website, Redcap uses a MySQL database via a secure web interface with data checks used during data entry to ensure data quality. REDCap includes a complete suite of features to support HIPAA compliance, including a full audit trail, user-based privileges, and integration with the institutional LDAP server. The MySQL database and the web server will both be housed on secure servers operated by the University of Minnesota Academic Health Center's Information Systems group (AHC-IS).

The phone counseling sessions will be audio-recorded. The audio recording devices will be stored in a locked file cabinet that only study staff have access to. The recordings will be uploaded and stored in Box where only study personnel will have access to them. As described on the UMN Box Secure Storage website, Box is a secure environment delivered by the Center of Excellence for HIPAA Data intended for storing, sharing and accessing sensitive and private-highly restricted files. The security of Box includes encryption, activity logging, Duo Two-Factor Authentication, and access controls such as view-only access. After uploading the sessions, they will be deleted from the audio recording device.

17.0 Provisions to Monitor the Data to Ensure the Safety of Participants

17.1 Data Integrity Monitoring.

This study involves no more than minimal risk. The study team, including the PI, Co-PI, and study coordinator will all be involved in monitoring the data to ensure the safety of the participants. We will ensure participants are fully aware of the expectations of participating in the study during the enrollment and consent process. The minimal risks associated with the study will be clearly outlined. Data will be reviewed for completeness, counseling sessions will be reviewed for accuracy and competence. Any adverse reactions to the NRT or the counseling sessions will be monitored and recorded and adjustments made for individual participants when necessary.

17.2 Data Safety Monitoring. This purpose of this study is not to diagnose or evaluate psychiatric symptoms or behaviors. That being said, if study staff observe a participant acting in a way that causes concern for either the physical or mental health of the participant or others, the staff will report this to [name], whom we have added to the study team with the specific responsibility of monitoring for worsening symptoms. If warranted, [name] will contact the participant to determine if they should be referred for help. If there is an immediate medical emergency, study staff will call 911. All paper data will be stored in locked file cabinets and all digital data will be stored in UMN Secured BOX or REDCap to which only study team members who need to use the data will have access.

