4.2 Biosafety: N/A

4.3 Stem Cells: N/A

5.0 Procedures Involved

5.1 Study Design:

This is a randomized clinical trial that will enroll patients with documented SMI (ICD-10 codes) including schizophrenia, any other psychotic disorder, bipolar I and II disorder, and/or recurrent/chronic major depressive disorder into either a counseling intensive smoking cessation program or the control group.

5.2 Study Procedures:

This intervention is tailored to the needs of SMI smokers including addressing barriers to quitting and the need for continued supportive contact. Following is an outline of the study procedures:

Baseline assessment

Trained study staff will:

- Conduct informed consent
- Collect demographic and smoking history information along with current interest in quitting, readiness to quit, confidence in ability to quit, and nicotine dependence. We also will include mood, general psychiatric health, and quality of life questionnaires. (SMI Smokers BL Interview V1.1, SMI Smokers BL Self Report V1.1)
- Collect the name and phone number of an additional contact. Study staff will call the contact in the case of an emergency with the participant or if staff are unable to reach the participant for study visits. Staff will explain the two reasons for needing the additional contact person to the participant during the baseline visit.
- Randomize participants: prior to the baseline visit, we will complete a 1 to 1 non-stratified randomization. The randomization results will be put in envelopes to be opened during the baseline visit, determining if a participant will be allocated to the intervention or the control group.
- Conduct or schedule session one with those in the intervention group
- Distribute materials/resources to all participants.

Follow up assessments:

- Conducted at 8 weeks and 6 months post baseline assessment. (SMI Smokers 8 Week Interview V1.0, SMI Smokers 6 Month Interview V1.0,

and SMI Smokers 8W 6M Self Report V1.0, Study Satisfaction Survey V1.0 will be administered only at the 6 month assessment and only to participants in the Intervention group).

- Conducted in person when possible, but a phone option will be available.
- Measures will include current smoking status, quit attempts, self-reported number of cigarettes per day for those who currently are smoking, and interest and confidence in quitting/continued abstinence.
- Reported 7-day abstinence at 8 weeks and 6 months will be validated by an expired carbon monoxide sample.

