The intervention group activities include the following:

Session 1:

- 1 hour in person visit
- Will include population specific information about smoking and mental illness
- Counselor will provide a strong and personalized recommendation to quit
- The remainder of Session 1 will be guided by current clinical practice guidelines and the National Cancer Institute's Clearing the Air patient workbook
 - The counselor will cover: past attempts to quit (reframing these as learning opportunities), and education on the risks of smoking and benefits of quitting both in general and for SMI patients.
 - Emphasis will be placed upon personal reasons for quitting or reducing number of cigarettes, especially those that are intrinsic
 - The counselor will discuss coping strategies and will focus on identifying strategies that are appropriate for the individual patient.
 - The counselor will provide tips for how to elicit support and for managing cravings
 - The counselor will address planning for behavior change including preparation for a quit date when applicable and anticipating challenging situations
- For those patients who initially choose to reduce rather than quit, the focus will be on reduction strategies including substituting NRT lozenge for individual cigarettes
- Patients who want to quit will be offered a nicotine patch and/or the nicotine lozenge.
- The counselor will review correct placement and/or use.
- Counselor also will address the efficacy and safety of nicotine replacement

Follow up counseling calls:

- Counselors will make 6 calls over 8 weeks after initial in person session.
- There will be assessments of current smoking status, NRT use and side

effects, and motivation to continue/restart quitting/reduction plan. NRT use will be encouraged.

- For those who have discontinued use or who have encountered problems with NRT, the counselor will review the patient's experience and consider alternatives including advice to try a different form of NRT
- If the patient is abstinent, the counselor will reinforce their success, discuss any times since the previous session when the participant struggled with cravings, will review strategies for managing triggers and cravings, and problem solve upcoming challenges to continued abstinence.

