- If the patient is smoking, the counselor will reinforce any efforts that the patient made including cutting down or attempting to quit and will apply brief motivational strategies to prompt further reduction or a subsequent quit attempt.
- The counselor will seek to keep all patients engaged in active behavior change.

Additional counseling phone calls:

- 3 calls (minimum) from 8 weeks to 6 months
- Telephone calls will be supplemented by supportive text messages when agreed to by participants during this phase.
- Those who choose to initiate a new quit/reduction attempt will be eligible for multiple telephone calls (up to six in one or more new rounds of intervention before the end of 6 months).

The control group activities include the following:

Participants in the control group will complete the baseline assessment interview and self-report and follow-up assessments at 8 weeks and 6 months. They will also receive information about smoking and mental illness and referrals to the QUITPLAN helpline.

Contact Letters

Participants in both the intervention and control groups will receive three letters by mail from the study. The first letter will be mailed approximately four weeks post baseline, the second approximately six weeks post 8-week assessment, and the last letter will be mailed approximately 12 weeks post 8-week assessment (Contact Letters V1.0)

5.3 Study Duration:

This study will enroll participants beginning fall of 2018 and continue enrollment until we recruit 60 participants or until time will no longer allow us to recruit based on the funding deadlines. As this is a two-year grant with no opportunity for a no-cost extension, all study related activities should be completed within two years.

5.4 Individually Identifiable Health Information:

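### Psychiatric worsening is found mainly by staff observation, with at least 11 planned contacts after baseline in the intervention arm against 2 in control, so event counts are comparable only at the two shared assessments

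*Combined protocol and SAP*

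**What the plan says.** Section 17.2 opens by limiting the study's scope: "This purpose of this study is not to diagnose or evaluate psychiatric symptoms or behaviors". It then provides that a concern is passed to a team member responsible for watching for worsening symptoms "if study staff observe a participant acting in a way that causes concern for either the physical or mental health of the participant". No scheduled psychiatric check is described there. Section 17.1 adds that "Any adverse reactions to the NRT or the counseling sessions will be monitored and recorded".

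In section 5.2 the baseline visit does measure mental state: "We also will include mood, general psychiatric health, and quality of life questionnaires". For the 8-week and 6-month assessments the text reads "Measures will include current smoking status, quit attempts, self-reported number of cigarettes per day for those who currently are smoking", followed by interest and confidence in quitting. A follow-up self-report form (SMI Smokers 8W 6M Self Report V1.0) is named, but its items are not shown. No outcome in 3.1 or 3.2 uses a psychiatric score.

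Contact after baseline differs by arm. The intervention arm has Session 1 ("1 hour in person visit"), then "Counselors will make 6 calls over 8 weeks after initial in person session", then "3 calls (minimum) from 8 weeks to 6 months", and the two assessments. The control arm has the two assessments. Both arms are mailed three letters.

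Section 12.1 allows the investigators to withdraw a participant who has an active psychotic episode or is hospitalized for suicidality. Sections 12.2 and 12.3 stop new data collection after withdrawal or termination.

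**The concern.** When events are found by noticing them, the number found depends on how often someone is looking. Here the looking is built into one arm's treatment. Equal true rates of worsening would give more recorded events in the intervention arm, and a reader of the pilot could take that as harm from quitting or from NRT. In control, worsening could go unnoticed until the next assessment.

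There is a second route. An investigator can withdraw a participant only for an event that has become known. Unequal detection can therefore produce unequal withdrawal, which touches retention (a feasibility aim in section 1.1) and leaves abstinence data missing by arm. Section 15.3 includes all randomized participants but states no rule for missing outcomes, and section 15.1 intends the effect estimates for planning a larger trial.

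**Working it through.** The documents state no contact total and no psychiatric event rate, so there is no figure to reproduce.

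**Step 1: planned staff contacts after the baseline visit** (section 5.2)

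| | Intervention | Control |
|---|---|---|
| Session 1 | 0 or 1 | 0 |
| Calls to week 8 | 6 | 0 |
| Calls, week 8 to month 6 | at least 3 | 0 |
| Assessments at 8 weeks and 6 months | 2 | 2 |
| Total | at least 11 or 12 | 2 |

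Session 1 counts as 0 or 1 because section 5.2 lets it be held at the baseline visit or scheduled for later. The totals are 6 + 3 + 2 = 11, or 12 with a separate Session 1. The ratios are 11/2 = 5.5 and 12/2 = 6.0. Apart from the assessments themselves, the split is 6 or 7 against 0 up to week 8, and at least 3 against 0 from week 8 to month 6. The letters are one-way mail and are not counted. Text messages, and the up to six further calls for a new attempt, are also left out; both would widen the gap.

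**Step 2: what this could do to event counts** (illustration; every input except the schedule is an assumption)

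Assume an episode begins uniformly over 26 weeks and lasts D weeks. Each contact falling inside the episode notices it independently with probability q, the same by phone or in person. With n contacts inside the episode, detection is the average over onset times of 1 − (1 − q)^n. Only contacts inside the episode count, so a short episode does not get 11 chances. Calls are evenly spaced: six before week 8, then weeks 12.5, 17 and 21.5. Assessments are at weeks 8 and 26.

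With q = 1 the result can be checked by hand:
- Control: 2D/26, so 2/26 = 8%, 8/26 = 31% and 16/26 = 62% for D = 1, 4 and 8.
- Intervention with 11 contacts: 11/26 = 42% for D = 1; (8 + 4 × 4)/26 = 24/26 = 92% for D = 4; 100% for D = 8.

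Detection, intervention v control (ratio):

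| q | D = 1 week | D = 4 weeks | D = 8 weeks |
|---|---|---|---|
| 1.0 | 42% v 8% (5.5) | 92% v 31% (3.0) | 100% v 62% (1.6) |
| 0.5 | 21% v 4% (5.5) | 56% v 15% (3.6) | 73% v 31% (2.4) |
| 0.25 | 11% v 2% (5.5) | 32% v 8% (4.2) | 46% v 15% (3.0) |

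A separate Session 1 in week 1 changes the intervention figures by about 1 percentage point at most. Over this grid, equal true rates would look 1.6 to 5.5 times higher in the intervention arm. The direction is the same in every cell; the size rests on the assumptions.

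**Step 3: withdrawal**

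The chain is: event noticed, possible withdrawal (12.1), no further data (12.2 and 12.3), missing outcome in the section 15.3 model. The documents give no frequency for any link, so no size is attached.

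**Step 4: could about 30 per arm support a test, even with equal ascertainment?**

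Normal approximation, two-sided 5%, n = 30 per arm: power = Φ{[|p2 − p1| − 1.96·√(2p̄(1 − p̄)/n)] / √([p1(1 − p1) + p2(1 − p2)]/n)}.
- 10% v 20%: (0.10 − 1.96 × 0.0922)/0.0913 = −0.88, power 19%.
- 20% v 40%: (0.20 − 1.96 × 0.1183)/0.1155 = −0.28, power 39%.

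Descriptive reporting is all the sample supports.

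**The case against.** The strongest reply is that the plan makes no between-arm safety comparison. No aim, endpoint or analysis calls for one, and section 17.2 is a participant-protection procedure that applies to both arms, as does the crisis plan in section 23.1. Watching more closely the people who receive NRT and counseling is a natural result of treating them. This stands: the defect is unequal ascertainment, not a planned analysis that fails. It does not remove the problem, because section 17.1 commits to recording reactions and withdrawals will be counted under retention. Even purely descriptive counts would mislead.

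A reader might infer that the baseline psychiatric scales are not repeated. The documents do not support that. The follow-up form is not shown, and the list of measures is open-ended: it does not name continuous abstinence, which is a secondary outcome. What can be said is that repetition is not stated, and that no outcome, analysis or monitoring step uses such scores.

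A reader might also infer that control-arm worsening goes undetected and that safety cannot be compared at all. Both go too far. Controls are seen or phoned at 8 weeks and 6 months, and findings at those two points can be compared on the same footing.

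Three smaller points also stand. The contacts are planned, and how much counseling can be delivered is itself a study question. Withdrawal under 12.1 is discretionary and has narrow triggers. Questionnaires at two visits can miss short episodes in between, which is why the fix includes a question about the whole interval.

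**Conclusion.** The point holds as a matter of ascertainment. Staff contact after the baseline visit is planned at 5.5 to 6 times the control frequency, detection is passive, and recorded adverse reactions are tied to treatments that section 5.2 describes only for the intervention arm. Control-arm worsening is less likely to be noticed, or is noticed late. Counts by arm should not be set against each other unless restricted to the 8-week and 6-month assessments.

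The contact ratio follows from the schedule alone, if calls are made as planned. The 1.6- to 5.5-fold inflation is illustrative and depends on the assumed episode length and chance of noticing. Unequal withdrawal is possible but cannot be quantified. This does not undermine the feasibility purpose of the pilot; it is a correctable weakness in how safety information is gathered and would be read.

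**What to change.** - **Section 5.2:** at 8 weeks and 6 months, ask both arms one fixed question, worded identically, on psychiatric hospitalization or psychotic episode since the last assessment.
- **Section 5.2:** state whether the 8-week and 6-month self-report repeats the baseline mood, general psychiatric health and quality of life questionnaires in both arms. If it does not, add them.
- **Sections 3.2 and 15.1:** name the answers and the change in these scores as descriptive safety outcomes by arm, with no formal test.
- **Reporting:** list events seen only at counseling contacts separately, outside the between-arm comparison. Beside that table, give investigator withdrawals by arm with the contact at which the event came to light, because someone withdrawn before an assessment cannot answer its question.

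No referral or withdrawal rule changes. The cost is a few minutes of added questionnaire time at two existing visits for about 60 people, plus one table. The protocol version is dated July 2019 and enrollment was to begin in fall 2018, so participants already past a visit will lack the new item; the report should give the number asked at each assessment.

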18.0 Provisions to Protect the Privacy Interests of Participants

18.1 Protecting Privacy:

Study personnel will meet with participants in the ECRC building in private rooms designated specifically to the study. Participants will be encouraged to schedule their counseling phone calls at times that allow them to have privacy.

18.2 Access to Participants:

The UMN Department of Psychiatry Clinical Research Advocate has a pre-determined list of patients who have given written consent to be contacted about studies for which they are potentially eligible to participate. This list will be shared with the study team through Secure Box for recruitment and screening purposes. If medical records need to be reviewed as part of the recruitment process, [name] is able to do that.

19.0 Compensation for Research-Related Injury

19.1 Compensation for Research-Related Injury: N/A

19.2 Contract Language: N/A

20.0 Consent Process

20.1 Consent Process (when consent will be obtained):

All potential participants will give their written consent to participate in the study in a private study room in the ECRC building with a study staff member who has been trained on the enrollment and consenting SOP. There will be time between the initial contact with a potential participant and the consenting/enrollment/baseline session. All participants will have the opportunity to read the consent form and to ask any questions they may have. The study staff member will also review the form with all potential participants asking open-ended questions about the study to ensure understanding. As mentioned previously, we will also administer a brief quiz to potential participants during the consenting process to ensure they are able to give informed consent.

20.2 Waiver or Alteration of Consent Process (when consent will not be obtained): N/A.

20.3 Non-English Speaking Participants: N/A

20.4 Participants Who Are Not Yet Adults (infants, children, teenagers under 18 years of age): N/A

20.5 Cognitively Impaired Adults, or adults with fluctuating or diminished capacity to consent:

The target population for this study is adults who have a diagnosis of a severe mental illness (and who smoke). We will take all precautions necessary to ensure participants fully understand the purpose of the study, the requirements of participation, and the demands that participation may

place on them. We will mitigate any confusion about the study through a clear informed consent process that will include using the UCSD Brief Assessment of Capacity to Consent for Minimal Risk research. If a potential participant is deemed unable to provide informed consent, they will not be enrolled in the study.

20.6 Adults Unable to Consent: N/A

21.0 Setting

21.1 Research Sites:

Recruitment of potential participants will take place in HCMC and UMN clinics. Research procedures, including all in-person visits, will take place in the ECRC building.

21.2 International Research: N/A

22.0 Multi-Site Research: N/A

23.0 Resources Available

23.1 Resources Available:

[name] has experience in recruiting participants from the HCMC clinics and we have the support of the Clinical Research Advocate at the UMN clinics to assist in recruitment of patients. We have access to the patients attending UMN and HCMC smoking cessation and psychiatric clinics as our base for recruiting potential participants. We plan to recruit 60 into the study.

Study staff will be housed in the Division of Epidemiology and Community Health and ECRC. Within the Division, we have access to all needed office supplies, printers, and technical assistance. The division also offers administrative support for research projects. The study coordinator will also have space designated to the study at the ECRC building. This is where the all in-person visits will take place. The ECRC also has basic office support and resources available for study use. In addition, ECRC has an Emergency Response Team (ALERT) that responds to any emergency that may occur within the clinic. All study staff members have experience in conducting human subjects research and will be trained by the PI and/or the study coordinator on standard operating procedures that need to be followed for every aspect of the study.

We will be following the UMN Psychiatry Department's "Unanticipated Problem/Crisis Communication Plan for Research Activity" flowchart for any psychiatric issues that arise while we are meeting or speaking with our study participants. We will also be employing a clinically licensed UMN employee (TBD) who will provide psychiatric safety information and guidance to study staff.

